### 8.6.1. Protocol-Specified Serious Adverse Events

There are no protocol-specified SAEs in this study. All SAEs will be reported by the investigator as described in previous sections, and will be handled as SAEs in the safety database (see section on [Serious Adverse Event Reporting Requirements](#)).

### 8.6.2. Potential Cases of Drug-Induced Liver Injury

Abnormal values in aspartate aminotransferase (AST) and/or alanine aminotransferase (ALT) levels concurrent with abnormal elevations in total bilirubin level that meet the criteria outlined below in the absence of other causes of liver injury are considered potential cases of drug-induced liver injury (potential Hy's law cases) and should always be considered important medical events.

The threshold of laboratory abnormalities for a potential case of drug-induced liver injury depends on the subject's individual baseline values and underlying conditions. Subjects who present with the following laboratory abnormalities should be evaluated further to definitively determine the etiology of the abnormal laboratory values:

- Subjects with AST or ALT and total bilirubin baseline values within the normal range who subsequently present with AST or ALT values  $\geq 3$  times the upper limit of normal (X ULN) concurrent with a total bilirubin value  $\geq 2$  X ULN with no evidence of hemolysis and an alkaline phosphatase value  $\leq 2$  X ULN or not available;
- For subjects with preexisting ALT **OR** AST **OR** total bilirubin values above the ULN, the following threshold values should be used in the definition mentioned above:
  - For subjects with preexisting AST or ALT baseline values above the normal range: AST or ALT values  $\geq 2$  times the baseline values and  $\geq 3$  X ULN, or  $\geq 8$  X ULN (whichever is smaller).

Concurrent with

- For subjects with preexisting values of total bilirubin above the normal range: Total bilirubin level increased from baseline by an amount of at least 1 X ULN **or** if the value reaches  $\geq 3$  X ULN (whichever is smaller).

The subject should return to the investigational site and be evaluated as soon as possible, preferably within 48 hours from awareness of the abnormal results. This evaluation should include laboratory tests, detailed history, and physical assessment.

In addition to repeating measurements of AST and ALT, laboratory tests should include albumin, creatine kinase, total bilirubin, direct and indirect bilirubin, gamma-glutamyl transferase, prothrombin time (PT)/ international normalized ratio (INR), and alkaline phosphatase. A detailed history, including relevant information, such as review of ethanol, acetaminophen, recreational drug and supplement consumption, family history, occupational exposure, sexual history, travel history, history of contact with a jaundiced person, surgery, blood transfusion, history of liver or allergic disease, and work exposure, should be collected. Further testing for acute hepatitis A, B, or C infection and liver imaging (eg, biliary tract) may be warranted. All cases confirmed on repeat testing as meeting the laboratory criteria defined above, with no other cause for liver function test (LFT) abnormalities identified at the time, should be considered potential Hy's law cases irrespective of availability of all the results of the investigations performed to determine etiology of the abnormal LFTs. Such potential Hy's law cases should be reported as SAEs.

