### 4.1. Inclusion Criteria

Subject eligibility should be reviewed and documented by an appropriate member of the investigator's study team before subjects are included in the study.

Subjects must meet all of the following inclusion criteria to be eligible for enrollment into the study:

1. Evidence of a personally signed and dated informed consent document indicating that the subject has been informed of all pertinent aspects of the study.
2. Subject is willing and able to comply with scheduled visits, treatment plan, laboratory tests, and other study procedures.
3. Male or female,  $\geq 18$  years of age.
4. Weight is  $\geq 40$  kg at Screening;
5. Subject has cancer diagnosed as having metastasized to bone or has multiple myeloma.
6. Imaging confirmation of bone metastasis at Screening or within 120 days prior to the Screening visit according to local standard of care (eg, via bone scan, magnetic resonance imaging (MRI), computed tomography (CT) scan, or positron emission tomography-computed tomography (PET-CT) scan).
7. Subject is expected to require daily opioid medication throughout the course of the study.
8. Subject willing to not use prohibited medications (including NSAIDs) throughout the duration of the study (refer to [Section 5.8.1](#) for details regarding prohibited concomitant medications).
9. Average Pain Score  $\geq 5$  at Screening for the index bone metastasis cancer pain site (refer to [Section 6.1.1](#)).
10. Patient's Global Assessment of Cancer Pain must be "fair", "poor" or "very poor" at Screening.
11. Eastern Cooperative Oncology Group (ECOG) Performance Status Score of 0, 1, or 2 at Screening (refer to [Appendix 3](#)).
12. Adequate bone marrow function at Screening (confirmed by a repeat test if needed), as defined by:
  - a. Absolute Neutrophil Count (ANC)  $\geq 1,500/\text{mm}^3$  or  $\geq 1.5 \times 10^9/\text{L}$ ;
  - b. Platelets  $\geq 100,000/\text{mm}^3$  or  $\geq 100 \times 10^9/\text{L}$ ;
  - c. Hemoglobin  $\geq 9.0$  g/dL.
13. Adequate renal function at Screening (confirmed by a repeat test if needed), as defined by:
  - a. Estimated glomerular filtration rate  $\geq 30$  mL/min as calculated by the Central Laboratory, and

- b. Urinary protein <2+ by urine dipstick performed by the Central Laboratory. If dipstick is  $\geq 2+$ , then 24 hour urinary protein <2 g per 24 hours.
14. Adequate liver function at Screening (confirmed by a repeat test if needed), as defined by:

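### Section 8.6.2 fixes the alkaline phosphatase cap at 2 x ULN although inclusion 14c admits 5 x ULN, so a subject whose measured value stays above 2 x ULN cannot meet the potential Hy's law criteria

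*Protocol*

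**What the plan says.** Protocol Section 8.6.2 opens by saying that the laboratory threshold for a potential drug-induced liver injury depends on the subject's "individual baseline values and underlying conditions".

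- **Normal baseline.** The criteria are AST or ALT of at least 3 x ULN with total bilirubin of at least 2 x ULN, "with no evidence of hemolysis and an alkaline phosphatase value" of at most 2 x ULN or not available.
- **Raised baseline ALT, AST or bilirubin.** Here "the following threshold values should be used in the definition mentioned above". New thresholds follow for AST/ALT and for bilirubin. None follows for ALP.

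Three consequences attach to meeting the criteria. Such cases "should always be considered important medical events". The subject is to return for evaluation, "preferably within 48 hours from awareness of the abnormal results". Cases confirmed on repeat testing, "with no other cause for liver function test (LFT) abnormalities identified at the time", are potential Hy's law cases, and such potential Hy's "law cases should be reported as SAEs".

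On eligibility (Section 4.1), criterion 5 requires that "Subject has cancer diagnosed as having metastasized to bone or has multiple myeloma". Criterion 14 allows bilirubin up to 1.5 x ULN (14a), AST and ALT up to 2.5 x ULN, or 5 x ULN with liver tumor (14b), and ALP up to 5 x ULN for everyone (14c).

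**The concern.** The section states a principle of adjusting to baseline and applies it to two of the three laboratory limits. The third is the one for which criterion 14 allows the widest departure from normal without any condition on liver involvement. A subject who enters at the 14c limit already fails the ALP condition on Day 1, before any drug effect is possible. If ALP simply stays where it was, a severe rise in ALT and bilirubin on treatment does not trigger Section 8.6.2.

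At stake are the automatic protections of that section. The exclusion follows from a rule that is definite as written, so it is not a detail left for another document to supply.

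**Working it through.** There is no power or alpha figure to reproduce. The check applies the Section 8.6.2 rules at the entry limits of criterion 14.

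**Structure of the rule.** A subject meets the laboratory criteria if all four hold: the AST/ALT threshold is reached, the bilirubin threshold is reached, there is no hemolysis, and ALP is at most 2 x ULN or not available.

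**Thresholds for a raised baseline b (in x ULN).**

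- Bilirubin: a rise of at least 1 x ULN or a value of at least 3 x ULN, whichever is smaller, so min(b + 1, 3).
- AST/ALT: at least 2 x baseline and at least 3 x ULN, or at least 8 x ULN, whichever is smaller, so min(max(2b, 3), 8).
- ALP: 2 at any baseline.

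| Test | Entry limit | Limit, normal baseline | Limit at the entry limit |
|---|---|---|---|
| Bilirubin (14a) | 1.5 | at least 2 | min(1.5 + 1, 3) = 2.5 |
| AST/ALT (14b) | 2.5 | at least 3 | min(max(2 x 2.5, 3), 8) = 5 |
| AST/ALT, liver tumor (14b) | 5 | at least 3 | min(max(2 x 5, 3), 8) = 8 |
| ALP (14c) | 5 | at most 2 | at most 2, unchanged |

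The bilirubin and AST/ALT limits stay above what criterion 14 admits (2.5 against 1.5; 5 against 2.5; 8 against 5). The ALP entry limit is 5 / 2 = 2.5 times the event cap.

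**Example.** Take ALP at 3 x ULN at entry and at the event, ALT 10 x ULN, bilirubin 4 x ULN, no hemolysis. ALT 10 exceeds 3, 5 and 8, and bilirubin 4 exceeds 2 and 2.5, so both conditions are met at any permitted baseline. ALP 3 exceeds 2, so the criteria are not met.

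**Does another reading avoid this?**

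- The adjusted thresholds are inserted into the same definition, so the ALP condition carries over.
- A subject with normal baseline AST, ALT and bilirubin but raised ALP falls under the normal-baseline rule, where the cap is explicit.
- The exception for an unavailable ALP helps only if a first, outside test omits it. ALP is in the study chemistry panel (Section 7.3.4) and in the Section 8.6.2 repeat tests on which a case must be confirmed.
- The sentence on baseline values and underlying conditions attaches no ALP rule.

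A subject admitted with high ALP whose value is at or below 2 x ULN at the event still qualifies.

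**Timing.** After Baseline, Section 7.3.4 schedules chemistry only at Weeks 16, 32 and 48 or at early termination. Liver events between draws would first appear clinically or on unscheduled tests.

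**The case against.** The strongest reply is that an eligibility limit and an event definition need not match. The cap is a deliberate part of the definition, and relaxing it trades specificity for sensitivity. The trial admits subjects with liver tumor, and criterion 14c sits among the liver-function criteria. The protocol nowhere says that raised ALP here comes from bone, or that GGT settles the question. A subject with raised ALP, ALT and bilirubin may have cholestasis or liver metastasis.

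This stands in part. The source of the ALP is a clinical matter that the protocol does not address. But the exclusion occurs whatever the source, including when ALP has not moved from baseline, and the section itself undertakes to take baseline into account. Recognized cholestasis or liver metastasis is still removed by the requirement that no other cause be identified.

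The second reply is that little is lost:

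- Section 8.5 makes an abnormal result an AE if it needs further diagnostic testing or changes dosing.
- Section 8.6 requires SAE reporting on medical judgment, and hospitalization is an SAE regardless. Section 8.14.1 then sets 24-hour notification.
- The sponsor and its risk management committee review blinded safety data, and the E-DMC reviews unblinded data (Sections 9.7 and 9.7.1.1).
- The suspension rule in Section 9.7.1.2 contains no ALP cap and does not cite 8.6.2.

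These backstops are real and limit the importance of the point. The SAE route, however, rests largely on judgment where Section 8.6.2 is automatic. The sponsor's blinded SAE review sees such a case only once it has been reported as serious.

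**Conclusion.** The concern holds. As written, Section 8.6.2 cannot classify a subject as a potential Hy's law case while measured ALP remains above 2 x ULN, and criterion 14c admits subjects at up to 5 x ULN. What is lost is the prompt evaluation, the automatic important-medical-event status and the SAE rule for confirmed cases.

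The protocol does not give the share of subjects with ALP above 2 x ULN or the chance of a liver event among them, so the number affected cannot be stated. No effect on efficacy inference or on the Section 9.7.1.2 suspension rule is claimed. The conclusion assumes only that the 8.6.2 criteria are applied literally and that ALP is measured at confirmation, as the section requires. The point should be corrected, because it concerns a liver-safety rule and the correction is small.

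**What to change.** Add one bullet to Section 8.6.2. For subjects with baseline ALP above 2 x ULN, the fixed ALP cap does not by itself exclude a case. Those who meet the AST/ALT and bilirubin criteria receive the 8.6.2 evaluation, with ALP judged against baseline and GGT used to help separate bone from liver origin. They count as potential Hy's law cases if confirmed on repeat testing with no other cause identified. Because the cap is simply no longer decisive for these subjects, no new ALP multiple is needed.

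A cross-reference from Section 9.7.1.2 is optional. It should be added only together with this bullet, since it would otherwise import the ALP cap into a rule that has none.

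The cost is one bullet and no new procedure: ALP and GGT are already in the chemistry panel and among the repeat tests. The downside is a few extra evaluations and some added risk of a temporary suspension for a case later explained by cholestasis or liver metastasis. Section 8.6.2 asks only that no other cause be known at the time, and Section 9.7.1.2 suspends dosing in all ongoing tanezumab studies on two reported events, before the relationship to drug is established. The protocol gives no basis for sizing that risk.

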### **8.7. Hospitalization**

Hospitalization is defined as any initial admission (even less than 24 hours) in a hospital or equivalent healthcare facility or any prolongation of an existing admission. Admission also includes transfer within the hospital to an acute/intensive care unit (eg, from the psychiatric wing to a medical floor, medical floor to a coronary care unit, or neurological floor to a tuberculosis unit). An emergency room visit does not necessarily constitute a hospitalization; however, the event leading to the emergency room visit should be assessed for medical importance.

Hospitalization does not include the following:

- Rehabilitation facilities;
- Hospice facilities;
- Respite care (eg, caregiver relief);
- Skilled nursing facilities;
- Nursing homes;
- Same-day surgeries (as outpatient/same-day/ambulatory procedures).

Hospitalization or prolongation of hospitalization in the absence of a precipitating, clinical AE is not in itself an SAE. Examples include:

- Admission for treatment of a preexisting condition not associated with the development of a new AE or with a worsening of the preexisting condition (eg, for workup of persistent pre-treatment laboratory abnormality);
- Social admission (eg, subject has no place to sleep);
- Administrative admission (eg, for yearly physical examination);

- Protocol-specified admission during a study (eg, for a procedure required by the study protocol);
- Optional admission not associated with a precipitating clinical AE (eg, for elective cosmetic surgery);
- Hospitalization for observation without a medical AE;
- Preplanned treatments or surgical procedures. These should be noted in the baseline documentation for the entire protocol and/or for the individual subject;

Diagnostic and therapeutic noninvasive and invasive procedures, such as surgery, should not be reported as AEs. However, the medical condition for which the procedure was performed should be reported if it meets the definition of an AE. For example, an acute appendicitis that begins during the AE reporting period should be reported as the AE, and the resulting appendectomy should be recorded as treatment of the AE.

### 8.8. Severity Assessment

If required on the AE CRFs, the investigator will use the adjectives MILD, MODERATE, or SEVERE to describe the maximum intensity of the AE. For purposes of consistency, these intensity grades are defined as follows:	
MILD	Does not interfere with subject's usual function.
MODERATE	Interferes to some extent with subject's usual function.
SEVERE	Interferes significantly with subject's usual function.

Note the distinction between the severity and the seriousness of an AE. A severe event is not necessarily an SAE. For example, a headache may be severe (interferes significantly with the subject's usual function) but would not be classified as serious unless it met one of the criteria for SAEs, listed above.

### 8.9. Causality Assessment

The investigator's assessment of causality must be provided for all AEs (serious and nonserious); the investigator must record the causal relationship in the CRF, as appropriate, and report such an assessment in accordance with the SAE reporting requirements if applicable. An investigator's causality assessment is the determination of whether there exists a reasonable possibility that the investigational product caused or contributed to an AE; generally the facts (evidence) or arguments to suggest a causal relationship should be provided. If the investigator does not know whether or not the investigational product caused the event, then the event will be handled as "related to investigational product" for reporting purposes, as defined by the sponsor (see the section on [Reporting Requirements](#)). If the investigator's causality assessment is "unknown but not related to investigational product," this should be clearly documented on study records.

In addition, if the investigator determines that an SAE is associated with study procedures, the investigator must record this causal relationship in the source documents and CRF, as appropriate, and report such an assessment in accordance with the SAE reporting requirements, if applicable.

### **8.10. Exposure During Pregnancy**

For both unapproved/unlicensed products and for marketed products, an exposure during pregnancy occurs if:

1. A female becomes, or is found to be, pregnant either while receiving or having been exposed (eg, because of treatment or environmental exposure) to the investigational product; or the female becomes, or is found to be pregnant after discontinuing and/or being exposed to the investigational product;
2. An example of environmental exposure would be a case involving direct contact with a Pfizer product in a pregnant woman (eg, a nurse reports that she is pregnant and has been exposed to chemotherapeutic products).
3. A male has been exposed (eg, because of treatment or environmental exposure) to the investigational product prior to or around the time of conception and/or is exposed during his partner's pregnancy.

If a study subject or study subject's partner becomes or is found to be pregnant during the study subject's treatment with the investigational product, the investigator must submit this information to the Pfizer drug safety unit on a serious adverse event (SAE) Report Form and an Exposure During Pregnancy (EDP) supplemental form, regardless of whether an SAE has occurred. In addition, the investigator must submit information regarding environmental exposure to a Pfizer product in a pregnant woman (eg, a subject reports that she is pregnant and has been exposed to a cytotoxic product by inhalation or spillage) using the EDP supplemental form. This must be done irrespective of whether an AE has occurred and within 24 hours of awareness of the exposure. The information submitted should include the anticipated date of delivery (see below for information related to termination of pregnancy).

Follow-up is conducted to obtain general information on the pregnancy and its outcome for all EDP reports with an unknown outcome. The investigator will follow the pregnancy until completion (or until pregnancy termination) and notify Pfizer of the outcome as a follow-up to the initial EDP supplemental form. In the case of a live birth, the structural integrity of the neonate can be assessed at the time of birth. In the event of a termination, the reason(s) for termination should be specified and, if clinically possible, the structural integrity of the terminated fetus should be assessed by gross visual inspection (unless preprocedure test findings are conclusive for a congenital anomaly and the findings are reported).

If the outcome of the pregnancy meets the criteria for an SAE (ie, ectopic pregnancy, spontaneous abortion, intrauterine fetal demise, neonatal death, or congenital anomaly [in a live born baby, a terminated fetus, an intrauterine fetal demise, or a neonatal death]), the investigator should follow the procedures for reporting SAEs.

- Additional information about pregnancy outcomes that are reported as SAEs follows:
- Spontaneous abortion includes miscarriage and missed abortion;
- Neonatal deaths that occur within 1 month of birth should be reported, without regard to causality, as SAEs. In addition, infant deaths after 1 month should be reported as SAEs when the investigator assesses the infant death as related or possibly related to exposure to the investigational product.

Additional information regarding the exposure during pregnancy may be requested by the investigator. Further follow-up of birth outcomes will be handled on a case-by-case basis (eg, follow-up on preterm infants to identify developmental delays). In the case of paternal exposure, the investigator will provide the study subject with the Pregnant Partner Release of Information Form to deliver to his partner. The investigator must document in the source documents that the subject was given the Pregnant Partner Release of Information Form to provide to his partner.

#### **8.10.1. Additional Postnatal Development Follow-Up**

The investigator will be asked to assist with collection of assessments of postnatal development as part of a separate protocol. Participation in that protocol is optional and will require that the subject review, agree and sign a separate informed consent document specific to that study, explaining the details of the post-partum follow-up for the subject and the newborn to participate in these assessments of postnatal development.

#### **8.11. Occupational Exposure**

An occupational exposure occurs when during the performance of job duties, a person (whether a healthcare professional or otherwise) gets in unplanned direct contact with the product, which may or may not lead to the occurrence of an adverse event.

An occupational exposure is reported to the drug safety unit within 24 hours of the investigator's awareness, using the SAE eport form, regardless of whether there is an associated AE/SAE. Since the information does not pertain to a subject enrolled in the study, the information is not reported on a Case Report Form (CRF), however a copy of the completed SAE report form is maintained in the investigator site file.

#### **8.12. Withdrawal Due to Adverse Events (See Also the Section on Subject Withdrawal/Early Termination)**

Withdrawal due to AE should be distinguished from withdrawal due to other causes, according to the definition of AE noted earlier, and recorded on the appropriate AE CRF page.

When a subject withdraws because of an SAE, the SAE must be reported in accordance with the reporting requirements defined below.

